5.2 Rationale for Trial Design

The purpose of the prophylaxis arm *in the Main Phase* is to provide sufficient exposure to N8-GP to evaluate immunogenicity and to provide efficacy data from 50-100 EDs of prophylaxis treatment with N8-GP in approximately 105(145) (see section 18.5) patients with severe haemophilia A ≥ 12 years. The reason for not having a prophylaxis control is that no FVIII product is globally approved for prophylaxis treatment.

...

The purpose of continuing all patients in the prophylaxis arm in the *Main Phase of the* trial until the last patient has completed at least 50 EDs of N8-GP is to ensure that the average exposure to N8-GP will be above 1 year for a considerable portion of the patients.

...

For clinical efficacy of N8-GP in the prevention of bleeding episodes, historical data on annualised bleeding frequency during on-demand treatment and prophylaxis will be used for comparison. The historical data derive from a recent review by an independent board of haemophilia treaters within the Swedish Council on Health Technology Assessment, including all published clinical studies on treatment of severe haemophilia A during the last 25 years which were comprised of at least 20 patients¹⁰. The review selected in total 37 separate studies of haemophilia A replacement therapy, seven of which contained data on bleeding frequency in an adult and/or adolescent population¹¹.

The part 1 of the Extension Phase will include 4 treatment arms: prophylaxis treatment every 4 day, a randomised sub-group of treatment every 4 or every 7 day, or on-demand treatment. The primary aim of part 1 of the Extension Phase is to investigate the safety and efficacy of every 7 day dosing of N8-GP. In the interest of patient safety this treatment will be offered only to a sub-set of patients who have low bleeding rates (see section 5.1) from prophylaxis treatment in the Main Phase. In order to control for season effects, subjects will continue with every 4 day dosing as control group in the randomised group. Allocation to the treatment arms will be done by randomisation. Subjects who do not wish to be randomised can continue in the Extension Phase part 1 with the treatment regimen from the Main Phase. This ensures that patients with low bleeding rate, who are not willing to be on every 7 day treatment, can stay in the trial in the non-randomised arm.

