8.1.3.2 Visit 2b for Patients on Prophylaxis Undergoing PK Evaluation

The second dose of N8-GP will be administered at the site after the last PK sample is taken.

Patients will be provided with an eDiary and will be carefully trained in the use of this eDiary including instruction in reporting details of bleeding episodes and prophylactic treatment including doses administered at all visits after Visit 2b.

Four days after first dose the following assessments will be performed and/or recorded in the eCRF

- Withdrawal criteria, see section 6.5
- AEs: before and after dosing, see section 12.1
- *e-Diary training, see section 5.3 and 8.4.3*
- *e-Diary dispensing*
- ~~• eDiary data review and rate severity of bleeding episodes 8.2.1~~
- Home treatment/e-Diary training, see section 5.3 and 8.4.3
- Drug accountability for the trial medication dispensed or returned from the previous visits must be recorded in IV/WRS, see section 10.

.....

8.1.4 Visit 14-n and EOT Visit- visit in the Extension Phase of the trial

Before any trial related procedures/activities related to the Extension Phase of the trial, the patient and/or the LAR must have signed the informed consent form after having received written and verbal information about the Extension Phase part of the trial.

It should be decided if the patient is eligible to be part of the randomised group in part 1 of the Extension Phase before the patient comes for Visit 13 (EOM) and 14. If the patient for the last 6 months (180 days) prior to Visit 13/14 only has had 0 - 2 bleeding episode the patient is eligible for randomisation. If the patient is eligible to be in the randomised part of the Extension Phase part 1 and the patient has agreed to be part of the randomisation group, the patient should give written consent through the informed consent addendum so agreement to randomisation is documented. Recruitment into the sub-group of the Extension Phase part 1 will stop approximately at mid-May

2014, hereafter also patients with a low bleeding rate will continue the same treatment as in the Main Phase.

When patients randomised in part 1 have completed the part 1, all patients can start part 2 at their next visit beginning at visit 17. Skipping visit 15 and/or 16 should be entered with a comment in EDC.

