18.10 Analyses of Extension Phase Data

Data from part 1 of the Extension Phase

*The main objective of part 1 of the Extension Phase is to investigate the safety and efficacy of every 7 day dosing by evaluating ABR for this dosing regimen and comparing it to the same historical bleeding episode rates as used in the primary analysis for the co-primary efficacy endpoint in the Main Phase. Prophylactic effect of every 7 day dosing will be concluded if the bleeding rate is significantly below 50% of the historical on-demand bleeding rate (i.e. significantly lower than 12) as well as within 25% of the historical prophylaxis bleeding rates (i.e. significantly lower than $6.8 * 1.25 = 8.5$). Since both must be met in practice it must be shown that the bleeding rate is significantly lower than 8.5.*

An analysis similar to that for the co-primary endpoint in the Main Phase will be carried out for the bleeding episodes in the two randomised treatment regimens during the Extension Phase part 1, adding treatment regimen as a factor to the model. Subjects switching from the every 7 day dosing arm to the non-randomised every 4 day dosing arm will be handled as withdrawals in this analysis. The imputation for withdrawals will be similar to that for the Main Phase, except that planned maximum duration is now 6 months.

Estimates of the annualised bleeding rates for each randomised regimen will be provided with 95% confidence intervals. Prophylactic effect of every 7 day dosing will be concluded if the upper limit of the 95% CI is below 8.5. In addition, the two randomised treatment regimens will be compared by reporting the estimated ratio between the two randomised treatment regimens with corresponding 95% confidence interval.

As for the co-primary endpoint in the Main Phase, a sensitivity analysis will be carried out where bleeding episodes for withdrawals are not imputed.

ABR based on accumulated number of bleeding episodes (Main Phase + Extension Phase part 1) will be evaluated for the every 4 day dosing regimens combined, i.e., combining the randomised and non-randomised arm. The model used will be the same as for the primary analysis of the Main Phase data.

Only treatment requiring bleeding episodes will be considered in the above evaluations of ABR

Incidence rate of FVIII-inhibitor and haemostatic effect of N8-GP when used for treatment of bleeding episodes will be evaluated based on accumulated data (Main Phase + Extension Phase part 1).

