1.1 Trial information

This phase 3 trial is a multi-centre, multi-national, open-label, non-randomised trial evaluating safety, pharmacokinetics and clinical efficacy of NNC 0129-0000-1003 (hereafter referred to as N8-GP) when used for treatment of bleeding episodes and for long-term prophylaxis. The trial consists of a Main Phase followed by an Extension Phase part 1 and part 2. In the main phase, patients in the prophylaxis arm were receiving one single bolus dose of 50 U/kg body weight (BW) of N8-GP every 4 days (96 hours interval).

In the extension part 1, patients with a low bleeding rate on every 4 day prophylaxis in the main phase have the possibility of being randomised to either 50 U/kg BW every 4th day or to 75 U/kg BW once weekly dosing. If the patient for the last 6 months (180 days) prior to Visit 13/14 only had 0 - 2 bleeding episodes, the patient was eligible for randomisation. Patients who were not eligible to be in the randomised arm or patients who are eligible but unwilling to be randomised can stay on the same regimen as in the Main phase.

In the extension phase part 2, patients with a low bleeding rate (0-2 bleeding episodes during the last 6 months) on every 4 day prophylaxis have the possibility of changing to 75 U/kg BW once weekly dosing regimen. Patients who has been on 75 U/kg BW once weekly dosing during extension phase part 1 can continue on this regimen arm or change back to either 50 U/kg BW every 4th day if the patients want to. Patients on once weekly dosing who have more than 2 spontaneous bleeds within a 8 week period or are hospitalised due to a bleed need to change back to every 4 days regimen according to the protocol.

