In the search, SBU identified 37 references dealing with “replacement therapy with factor concentrates in treating severe, moderate, and mild haemophilia A”. All these references identified by SBU were reviewed as full length articles at Novo Nordisk, and only the original papers with a mean total ABR reported (or at least possible to calculate) in patients with an endogenous FVIII:C activity <2% were included in our analysis.

Table 2–1 Historical mean total annual bleeding rate in Haemophilia A patients with an endogenous FVIII:C activity <2%

SBU Ref No	Reference	On-demand (mean ABR)	Number of patients	Prophylaxis (mean ABR)	Number of patients
4	Courter, 2001³	18	27	4	27
5	Lusher, 2003⁴	23	85	10	85
5	Lusher, 2003⁴	N.R.	N.R.	6	45
9	Tarantino, 2004⁵	N.R.	N.R.	6.3	107
10	Nemes, 2007⁶	N.R.	N.R.	4.9	49
11	Recht, 2009⁷	N.R.	N.R.	3.9	94
15	Abshire, 2000²	34	38	8.3	27
17	Smith, 2005^{*8}	N.R.	N.R.	10.3	32
18	Manco-Johnson, 2007¹	18	33	3.3	32
25	Schwartz, 1990^{**9}	19	56	N.R.	N.R.
	Weighted Mean	24	179	6.8	394

ABR = Annual Bleeding Rate. N.R. = not reported. Studies in *italics* have not included adults. No = Reference number in SBU report, chapter 3.1.1. * 5/32 are moderate Hemophilia A, **4/56 are moderate Hemophilia A

In the studies, the mean ABR in patients on prophylaxis is consistently lower than in patients treated on-demand, as expected. The studies have ABR in the range of 18 – 34 and 3.3 – 10, for on-demand and prophylaxis treatment, respectively, and include different numbers of subjects. To arrive at a representative ABR number from the various studies, we weighted the estimates from each study based on the number of subjects included.

As the proposed trial with N8-GP will only include patients aged 12 years and above, we further suggest to exclude 3 of the 9 historical studies^{1,3,4}, that only include children below age 6, in order to better reflect the study population. The historical mean ABR for on-demand and prophylaxis in haemophilia A with <2% will then be estimated at 24 and 6.8, respectively. However, if also the

studies including children below 6 years of age are included, the estimated ABR for on-demand and prophylaxis are 23 and 6.4, respectively. The 2% cut off is often used in clinical studies and will give a conservative estimate of the ABR in the study population in the proposed trial with a cut off of <1%.

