2.10 Analyses of Extension Phase Data

Data from part 1 of the Extension Phase

The main objective of part 1 of the Extension Phase is to investigate the safety and efficacy of every 7 day dosing by evaluating ABR for this dosing regimen and comparing it to the same historical bleeding episode rates as used in the primary analysis for the co-primary efficacy endpoint in the Main Phase. Prophylactic effect of every 7 day dosing will be concluded if the bleeding rate is significantly below 50% of the historical on-demand bleeding rate (i.e. significantly lower than 12) as well as within 25% of the historical prophylaxis bleeding rates (i.e. significantly lower than $6.8 \times 1.25 = 8.5$). Since both must be met in practice it must be shown that the bleeding rate is significantly lower than 8.5.

An analysis similar to that for the co-primary endpoint in the Main Phase will be carried out for the bleeding episodes in the two randomised treatment regimens during the Extension Phase part 1, adding treatment regimen as a factor to the model. Subjects switching from the every 7 day dosing arm to the non-randomised every 4 day dosing arm will be handled as withdrawals in this analysis.

The imputation for withdrawals will be similar to that for the Main Phase, except that planned maximum duration is now 6 months.

Estimates of the annualised bleeding rates for each randomised regimen will be provided with 95% confidence intervals. Prophylactic effect of every 7 day dosing will be concluded if the upper limit of the 95% confidence intervals (CI) is below 8.5. In addition, the two randomised treatment regimens will be compared by reporting the estimated ratio between the two randomised treatment regimens with corresponding 95% confidence interval.

As for the co-primary endpoint in the Main Phase, a sensitivity analysis will be carried out where bleeding episodes for withdrawals are not imputed.

ABR based on accumulated number of bleeding episodes (Main Phase + Extension Phase part 1) will be evaluated for the every 4 day dosing regimens combined, i.e., combining the randomised and non-randomised arm. The model used will be the same as for the primary analysis of the Main Phase data.

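### The 8.5/yr rule for weekly dosing speaks to an absolute rate in selected low bleeders; any comparison with 4-day dosing should rest on the randomised ratio, adjusted for prior bleeding rate

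*SAP*

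**What the plan says.** The decision rule for Q7D appears twice in the same form. SAP 2.10: "Prophylactic effect of every 7 day dosing will be concluded if the upper limit of the 95% confidence intervals (CI) is below 8.5". Protocol 18.10 (Amendment 13): "Prophylactic effect of every 7 day dosing will be concluded if the upper limit of the 95% CI is below 8.5". The limit is the Main Phase one, 6.8 x 1.25 = 8.5 bleeds per year.

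The historical 6.8 comes from published studies. The stated filter is a usable mean bleeding rate "in patients with an endogenous FVIII:C activity <2% were included in our analysis" (SAP 2.2.2). No filter on bleeding is stated.

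Entry to the randomised part is restricted by bleeding in the 180 days before Visit 13/14. A patient who "only had 0 - 2 bleeding episodes, the patient was eligible for randomisation" (SAP 1.1; the same criterion is in Protocol 8.1.4, Amendment 13). Allocation is 2:1, Q7D to Q4D, for 24 weeks.

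The plan gives the randomised Q4D arm a purpose: "In order to control for season effects, subjects will continue with every 4 day dosing as control group in the randomised group" (Protocol 5.2, Amendment 13). Regimen is a factor in the model, and SAP 2.10 adds: "In addition, the two randomised treatment regimens will be compared by reporting the estimated ratio between the two randomised treatment regimens", with a 95% confidence interval. No hypothesis or criterion is attached to that ratio.

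On missing time: "The imputation for withdrawals will be similar to that for the Main Phase, except that planned maximum duration is now 6 months" (SAP 2.10). Patients who switch from Q7D to the non-randomised Q4D arm are treated as withdrawals and their bleeds are imputed to 24 weeks (SAP 2.2.2). A sensitivity analysis without imputation is already planned.

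**The concern.** A limit derived from studies with no stated selection on bleeding is applied to patients chosen because they bleed little on Q4D. Such patients would be expected to sit well under 8.5 with no change of regimen. A pass is then partly a product of who was let in, and the rule cannot say how much is due to Q7D.

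Protocol 3.1.4 (Amendment 14) itself says that moving from Q4D to Q7D may bring more break-through bleeds. That is a question of Q7D against Q4D. The randomised Q4D arm can answer it, but the ratio enters no conclusion and carries no adjustment for prior bleeding. In its imputed form it also treats the arms differently: a regimen switch can occur, and be imputed, only on Q7D.

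**Working it through.** **1. The plan's own figures.** The historical prophylaxis mean, without the studies in children under 6, is (85x10 + 107x6.3 + 49x4.9 + 94x3.9 + 27x8.3 + 32x10.3)/394 = 2684.5/394 = 6.81, and 6.8 x 1.25 = 8.5. The only power stated for an 8.5 rule is the Main Phase 79%: Phi((8.5 - 7.0)/sqrt(7.0x5/120) - 1.96) = Phi(2.78 - 1.96) = 79%. Both reproduce. No sample size or power is stated for the Q7D rule.

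**2. What selection does to the expected rate.** Inputs: mean 6.8/yr and over-dispersion (OD) 5 from Protocol 18.1, and 0-2 bleeds in 180 days. Assumption: patient rates follow a gamma distribution and stay constant over time.

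- Shape k = 6.8/(5 - 1) = 1.7; gamma rate b = 1.7/6.8 = 0.25; t = 180/365.25 = 0.493 yr; p = b/(b + t) = 0.337.
- P(0) = p^1.7 = 0.157; P(1) = 1.7(1 - p)P(0) = 0.177; P(2) = (1.7x2.7/2)(1 - p)^2 P(0) = 0.159. Eligible: 0.493.
- A patient with n bleeds has expected future rate (k + n)/(b + t). Averaged over eligible patients: (1.7x0.157 + 2.7x0.177 + 3.7x0.159)/0.493/0.743 = 3.64/yr.
- 8.5/3.64 = 2.3. For OD 4 and OD 6 the expected rates are 4.06 and 3.31/yr and the multiples 2.1 and 2.6.

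**3. How the rule behaves.** Simulated: 24 weeks, 2:1 allocation, 20-40 Q7D patients, 50-100% of bleeds spontaneous (neither range is in the documents). A Q7D patient switches at the second spontaneous bleed within 8 weeks. Switchers are imputed to 24 weeks at the observed rate, or at 24/yr for the missing time if they switch within a month. The model is Pearson-scaled Poisson with regimen as a factor, and the arm-closure rule is applied. The severe-bleed criterion, investigator switches and other withdrawals are left out.

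| True Q7D rate against Q4D | Rate per year (OD 5) | Pass rate, OD 5 | Pass rate, OD 4-6 |
|---|---|---|---|
| Equal | 3.64 | 46-97% | 34-99% |
| +25% | 4.55 | 23-75% | 11-87% |
| +50% | 5.46 | 8-40% | 3-57% |
| Doubled | 7.28 | 0-4% | 0-9% |

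At a true rate of 8.5 the rule passes in 0-1% of trials. Arm closure lowers the pass rate by at most 1.3 points.

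**4. The ratio when the regimens are equal (OD 5).** Imputed, its median is 1.19-1.53; with 70% of bleeds spontaneous, about 1.25-1.30. A switch is triggered by a cluster of bleeds, and the imputation carries that cluster forward on Q7D only. Without imputation the median is 0.89-0.97, slightly low because frequent bleeders lose follow-up. The mean Q7D rate shows the same pattern: 4.4-5.4 imputed and 3.2-3.5 non-imputed, against a true 3.64.

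**5. What a covariate adds.** Main-phase time was assumed uniform over 7-27 months (Protocol 5.1, Amendment 14, gives about 7 to about 19 months with a maximum of about 27; SAP 2.2.2 gives 100 weeks as the maximum). Correlation with the patient's true rate is 0.77 for main-phase bleeds divided by time, 0.67 for the raw count and 0.44 for the 180-day count. Adjusting for the log rate narrows the imputed ratio's 95% interval from a factor of about 1.9-2.7 either side to about 1.8-2.4. It moves the non-imputed median to 0.96-1.00 when the regimens are equal; the 180-day count reaches only 1.86-2.60 on the imputed interval.

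**The case against.** The strongest reply is that the plan does not claim what it is faulted for. Part 1 is defined as a comparison with historical rates, and its conclusion is prophylactic effect, not similarity to Q4D. Selection is stated openly, was made for patient safety, and fits the aim of finding patients for whom weekly dosing is enough. All of this stands. A pass at +25% or +50% is no error against the 8.5 null.

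A reader might infer three stronger things that the documents do not support.

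- That the randomised Q4D arm has no role. Regimen is in the model, the ratio is reported with its interval, and the control has a stated season-effect purpose. It lacks a role only in the decision rule.
- That the rule is lax and a clearly worse regimen would usually pass. Simulated without switching or imputation, a +50% regimen passes in 82% of trials with 30 Q7D patients. The plan has both, and then the figure is 8-40%.
- That the historical patients were certainly unselected on bleeding. The documents give only the filter used to choose papers; enrolment criteria within those papers are not visible.

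It is also true that the SAP's stated scope is part 2, that part 1 was already reported when the SAP was dated, and that most of the remedy (ratio, interval, non-imputed analysis) is planned. That limits the point to interpretation and one covariate. It does not remove it: SAP 2.10 restates the 8.5 rule, and SAP 2 excepts conclusions on every-7-day dosing from those settled by the pivotal report.

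**Conclusion.** The point holds in a limited form. An upper limit below 8.5 supports an acceptable absolute rate on Q7D in patients selected for 0-2 bleeds in 180 days. It says little about Q7D against Q4D, because 8.5 is about 2.3 times (2.1-2.6) the rate those patients would be expected to have on Q4D. A fail is no clearer: with equal regimens the rule passes in only 46-97% of simulated trials, because Q7D switches are imputed.

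The planned randomised ratio is the right evidence on regimen, but it is unadjusted, and its imputed version is biased upward to about 1.2-1.5 when there is no difference.

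These sizes rest on gamma-distributed constant rates, the planning inputs (6.8/yr, OD 4-6), an assumed 20-40 Q7D patients and an assumed 50-100% spontaneous share. This is a cheap improvement of minor to moderate severity; it does not overturn the part 1 decision.

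**What to change.** In SAP 2.10, and in Protocol 18.10 if it is revised:

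1. Adjust the planned Q7D:Q4D ratio for log pre-randomisation bleeding rate, defined as (main-phase bleeds + 0.5) divided by main-phase time. The raw count is unsuitable because follow-up varies widely between patients.
2. Rest any statement about Q7D relative to Q4D on that ratio and its 95% interval. Give the already planned non-imputed version beside the imputed one, and note that Q7D-only switch imputation biases the imputed ratio upward.
3. State that an upper limit below 8.5 concerns the absolute bleeding rate in selected low bleeders.
4. Set no margin on the ratio; the design was not sized for one. Requiring an upper limit below 1.25 would have about 12% power at a true ratio of 1 with 30:15 patients, even without switching or imputation.
5. Label the analysis post hoc.

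The cost is some wording and one covariate from data already collected. The downsides are real: the covariate is chosen after the fact, and the ratio stays imprecise, with an interval roughly a factor of 1.7-2.4 either side for 20-40 Q7D patients. At a true +50%, the adjusted non-imputed interval lies above 1 in only 8-23% of trials. The adjusted imputed interval does so in 28-78%, but also in 3-16% when the regimens are equal, against a nominal 2.5%.
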